4.3.4 Retreatment Criteria

The subject may undergo a touch-up treatment 30 days after the initial treatment (ie, at the month 1 follow-up visit) if both the subject and TI determine that optimal correction has not been achieved and total treatment has been less than 4.0 mL. The total injection volume for an individual subject for the initial and touch-up treatments combined cannot exceed 4.0 mL.

Subjects in the treatment group may undergo repeat treatment 12 months after the last treatment (ie, at the month 12 follow-up visit after all procedures are completed). The total injection volume for repeat treatment cannot exceed 4.0 mL.

4.4 Permissible and Prohibited Medications/Treatments

4.4.1 Permissible Medications/Treatments

Topical anesthesia may be used during treatment according to routine practice, but it must be limited to the treatment areas only. Examples of permitted topical anesthesia include: ice, lidocaine cream, or both.

If a subject is on a regimen of over-the-counter or prescription, oral or topical, anti-wrinkle products below the subnasale, the regimen must have been stable for at least 30 days prior to study enrollment and the subject must continue with the regimen throughout the study.

The use of any concomitant medication, prescription or over-the-counter, is to be recorded on the subject's electronic case report form (eCRF) at each visit along with the reason the medication is taken.

Therapy considered necessary for the subject's welfare may be given at the discretion of the TI. If the permissibility of a specific medication/treatment is in question, please contact Allergan.

4.4.2 Prohibited Medications/Treatments

Subjects must not initiate or be on an existing regimen of anti-coagulant medications (eg, warfarin, clopidogrel) or other medications or substances known to increase coagulation time (eg, aspirin, ibuprofen, or herbal supplements) in the 10 days prior to undergoing study device injection and for 3 days afterward.

During the course of the study, subjects must not:

- be on an ongoing regimen of lidocaine or structurally-related local anesthetics
- be on an ongoing regimen of drugs that reduce or inhibit hepatic metabolism (eg, cimetidine, beta-blockers)
- be enrolled in another study and may not receive another investigational product in the 30 days prior to study enrollment
- receive permanent facial implants (eg, polymethylmethacrylate, silicone, polytetrafluoroethylene) anywhere in the face or neck
- receive facial tissue augmentation with fat injections below the subnasale; semi-permanent dermal fillers (eg, calcium hydroxyapatite, poly-L-lactic acid) in the chin or jaw; or dermal filler injections in the glabellar area, nose, lips, or perioral area
- receive botulinum toxin injections below the subnasale (including the masseter muscles)
- undergo mesotherapy or receive cosmetic facial procedures (eg, face-lift, brow lift, facial reconstructive surgery, laser, photomodulation, intense pulsed light, radio frequency, dermabrasion, moderate or greater depth chemical peel, or other ablative procedures) anywhere in the face or neck
- undergo allergen desensitization therapy
- undergo any piercing or tattooing procedures below the subnasale
- undergo any dental procedure (other than prophylaxis or dental fillings)

The decision to administer a prohibited medication/treatment is done with the safety of the study participant as the primary consideration. When possible, Allergan is to be notified before the prohibited medication/treatment is administered.

4.4.3 Escape Medications

Although several authors have reported that hyaluronidase (Vitrase™ or Amphadase®) is effective in reversing the effects of misplaced or excess HA-based dermal fillers, no hyaluronidase product has been approved for this indication. Therefore, administration of hyaluronidase for this use should not be performed during this study.

4.4.4 Special Diet or Activities

Within the first 24 hours after treatment, subjects should avoid strenuous exercise, extensive sun or heat exposure, and alcoholic beverages. Exposure to any of the above may cause temporary redness, swelling, and/or itching at the injection sites.

For 2 days after treatment, subjects should avoid unnecessary external compression of the treatment site that could cause displacement or indentation where the product has been placed. Subjects will be advised not to have a massage, enter a hot spring or sauna, receive excessive sun exposure, or go swimming during the week following study treatment (initial, touch-up, or repeat).

4.5 Treatment Allocation Ratio

Subjects are randomized at an allocation ratio of 3 treatment with JUVÉDERM VOLUMA XC to 1 control group.

5. Study Population

5.1 Number of Subjects

Up to 224 subjects will be enrolled at up to 15 sites.

5.2 Study Population Characteristics

Adult subjects with chin retrusion who are seeking to increase facial volume in the chin area will be recruited.

5.3 Inclusion Criteria

The following are requirements for entry into the study:

1. Age 22 or over and in good general health

[figure not shown]
3. Treating Investigator considers the subject's chin retrusion to be amenable to temporary correction

5.4 Exclusion Criteria

The following are criteria for exclusion from participating in the study:

1. Has ever received permanent facial implants (eg, polymethylmethacrylate, silicone, polytetrafluoroethylene) anywhere in the face or neck, or is planning to be implanted with any of these products during the study
2. Has ever undergone fat injections below the subnasale or is planning to undergo this procedure during the study
3. Has tattoos, piercings, facial hair (ie, beard, mustache), or scars below and including the subnasale that would interfere with visual assessment of the chin, jowls, or jawline
4. Has undergone semipermanent dermal filler treatment (eg, calcium hydroxyapatite, poly-L-lactic acid) in the chin or jaw within 36 months before enrollment or is planning to undergo such treatment during the study
5. Has undergone dermal filler injections, or has undergone any surgery in the chin or jaw area (including marionette lines, pre-jowl sulci, mandibular body, or masseter muscles) within 24 months before enrollment or is planning to undergo any of these procedures during the study
6. Has undergone dermal filler injection in the lips or perioral area within 12 months before enrollment or is planning to undergo such treatment during the study

10. Has undergone mesotherapy or cosmetic treatment (laser, photomodulation, intense pulsed light, radio frequency, dermabrasion, moderate or greater depth chemical peel, liposuction, lipolysis, or other ablative procedures) anywhere in the face or neck, or botulinum toxin treatment below the subnasale (including injections to the masseter muscles) within 6 months before enrollment or is planning to undergo any of these procedures during the study

6. Procedures

6.1 Washout or Run-In Intervals

the *Journal of the American Statistical Association* (1980, 75, 311-322) and the *Journal of the Royal Statistical Society, Series B* (1981, 43, 1-37). The latter paper is the most comprehensive treatment of the topic, and it is the source of the following summary.

6.1.2 Run-in Intervals

Run-in Intervals	Medication or Procedure
2 days before treatment	
 Prophylactic herpes treatment for subjects with a history of recurrent oral herpes lesions
30 days before enrollment	
 Over-the-counter or prescription, oral or topical, anti-wrinkle products below the subnasale for subjects who will use such products during the study

Approval Date: 01-Mar-2017

Approval Date: 01-Mar-2017

A series of horizontal black bars of varying lengths, likely representing data points or categories in a visualization. The bars are arranged vertically and have irregular, stepped ends, suggesting a histogram or a series of discrete measurements. The lengths of the bars vary significantly, with some being very short and others extending across most of the frame.

1

For more information, contact the Office of the Vice President for Research and Economic Development at [contact] or [contact].

11. **What is the primary purpose of the *Journal of Clinical Endocrinology and Metabolism*?**

For more information, contact the Office of the Vice President for Research and Economic Development at [contact] or [contact].

For more information, contact the Office of the Vice President for Research and Economic Development at [contact] or [contact].

Digitized by [contact]

For more information, contact the Office of the Vice President for Research and Economic Development at [contact] or [contact].

For more information, contact the Office of the Vice President for Research and Economic Development at [contact] or [contact].

© 2019 Pearson Education, Inc.

11. **What is the primary purpose of the `get` method in the `HttpURLConnection` class?**

For more information, contact the Office of the Vice President for Research and Economic Development at [contact] or [contact].

Page 1 of 1

10.1007/s00332-010-9000-0

For more information, contact the Office of the Vice President for Research and Economic Development at [contact] or [contact].

1000

For more information, contact the Office of the Vice President for Research and Economic Development at [contact] or [contact].

—
—

© 2013 Pearson Education, Inc.

Topic	Percentage
Smart homes	98
Smart cities	98
Smart grids	98
Smart transportation	98
Smart agriculture	98
Smart energy	98
Smart waste management	98
Smart water management	98
Smart buildings	98
Smart manufacturing	98
Smart healthcare	98
Smart education	98
Smart retail	98
Smart government services	98
The concept of a 'smart city'	60

The figure consists of a 10x10 grid of black bars. The bars are arranged in 10 rows and 10 columns. The first and last columns of bars are much taller than the others. The first row contains two very tall bars, while the last row contains two very short bars. The other 16 bars are of uniform height, filling the middle section of the grid.

6.3 Instructions for the Subjects

At the screening visit, the TI (or designee) will discuss alternative treatments that may be available with any subject who is interested in participating in the study; he/she will counsel the subject regarding his/her treatment goals and the potential benefits and limitations of study treatment. After counseling, if the subject's expectations are achievable within the parameters of the study, the TI (or designee) will proceed with obtaining the subject's signature on the ICF and will continue the subject in the study.

During each study visit, subjects will be required to remove all jewelry, make-up, and lipstick, and male subjects must be clean-shaven below the subnasale to avoid interference with digital imaging and evaluations of the chin and chin area.

To reduce the risk of posttreatment bleeding or bruising, subjects on a regimen of medications (eg, aspirin or ibuprofen) or other substances known to increase coagulation time (eg, herbal supplements with garlic or gingko biloba) must suspend the regimen for at least 10 days before and 3 days after study treatment (initial, touch-up, and repeat).

For at least 24 hours after treatment, subjects should avoid strenuous exercise, consumption of alcoholic beverages, and extended exposure to sun or heat to reduce the risk of posttreatment redness, swelling, and/or itching.

For 2 days after treatment, subjects should avoid unnecessary external compression to the treatment site that could cause displacement or indentation where the product has been placed. Subjects should also avoid having a massage, entering a hot spring or sauna, receiving excessive sun exposure, or going swimming during the week following study treatment (initial, touch-up, and repeat).

Subjects will also be instructed to contact the TI or his/her research staff to report any unexpected symptoms or to ask questions about the study.

6.4 Unscheduled Visits

An unscheduled visit may occur for safety purposes (eg, evaluation of AEs or ISRs as requested by the subject and/or TI). Applicable procedures will be performed and recorded on the eCRF.

An unscheduled visit may also occur to repeat facial digital images if those obtained at the scheduled visit are poor quality images.

6.5 Early Discontinuation of Subjects

Each subject reserves the right to withdraw from the study at any time without jeopardy to his/her future medical care. The month 12/early exit procedures are to be performed at the final study visit. Subjects may also be administratively withdrawn if they do not return for follow-up visits. For any subject who withdraws from the study, the date and reason for withdrawal will be recorded on the eCRF. If an AE is ongoing at the time of withdrawal and is related to the study treatment, the TI will attempt to follow the subject until the AE has

been resolved or follow-up is no longer possible. The TI shall ask for the subject's permission to follow his/her status/ condition outside the study.

If a subject fails to return for 1 or more scheduled study visits, the TI (or designee) will attempt to contact the subject to determine and document the reason the subject has failed to return, and to encourage compliance with the study visit schedule.

6.6 Withdrawal Criteria

If a subject has a positive urine pregnancy test at the time of the initial, touch-up, or repeat treatment visit, the subject will not be eligible for treatment and will be withdrawn from the study. The pregnancy will be followed as described in Section 10.3.

In addition, a subject must be withdrawn from the study if he or she:

- receives any dermal filler or fat injection to the chin area
- undergoes facelift or facial reconstructive surgery
- receives treatment with hyaluronidase in the chin area

7. Response Measures and Summary of Data Collection Methods

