10.3 Pregnancy

If a female becomes pregnant after treatment, the TI will notify Allergan immediately after the pregnancy is confirmed. The TI shall (1) instruct the subject to notify her physician of the presence of the investigational device and (2) follow the pregnancy to term. Best practices are to be followed in order to ensure the welfare of the subject and the fetus. The Medical Safety Physician will contact the TI to obtain information about the pregnancy outcome. The subject will continue to be followed as part of the mITT Population, but the pregnancy will be documented as a protocol deviation, and the subject will not be evaluated as part of the PP Population for timepoints after the pregnancy is confirmed.

Pregnancy by itself will not be considered an AE or serious adverse event (SAE). Hospitalization for a normal delivery or elective abortion of a normal fetus does not

constitute a SAE. However, the occurrence of an adverse pregnancy outcome for the mother or child may constitute an AE or SAE, and these are to be reported as described in Sections 11.1.3 and 11.1.4.

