11.1 Definitions

11.1.1 Adverse Event

An AE is defined in accordance with ISO 14155 as “any untoward medical occurrence, unintended disease or injury, or untoward clinical signs (including abnormal laboratory findings) in subjects, users, or other persons, whether or not related to the investigational medical device.” This definition includes events related to the investigational medical device or comparator and events related to the procedures involved except for events in users or other persons, which only include events related to investigational medical devices.

Disease signs and symptoms that existed prior to the study treatment are not considered AEs unless the condition recurs after the subject has recovered from the pre-existing condition or the condition worsens in intensity or frequency during the study.

AEs will be monitored throughout the study beginning with signing of the ICF. At each postscreening visit, the TI (or designee) will begin querying for AEs by asking each subject a general, non-directed question such as “Have you had any changes to your condition since your last visit?” Previous AEs and changes in therapy/concomitant medications are to be updated. Directed questioning and examination will then be done as appropriate. All reportable AEs and clinically significant abnormal laboratory findings will be documented on the appropriate eCRF.

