11.3 Procedures for Reporting an AE or ADE

All AEs or ADEs occurring during the study period (beginning with signing ICF) are to be recorded on the appropriate eCRF. Any AE that is ongoing at the exit visit must be followed up as appropriate.

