12.7 Testing of Biological Specimens

At screening and before each study treatment (initial and touch-up), a trained research staff member will perform pregnancy testing on urine samples of women of childbearing potential. The test employed should have a sensitivity of at least 50 mIU/mL for human chorionic gonadotropin.

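### Protocol 6.6 and 10.3 conflict for a subject who conceives after her initial injection and tests positive at touch-up: one withdraws her, the other keeps following her

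*Protocol*

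**What the plan says.** **Protocol 6.6 (Withdrawal Criteria)** covers a positive urine test at the initial, touch-up or repeat treatment visit. In each case "the subject will not be eligible for treatment and will be withdrawn from the study". It makes no exception for a subject who has already been injected. It refers to 10.3 only for how the pregnancy is to be followed.

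**Protocol 10.3 (Pregnancy)** covers a woman who becomes pregnant after treatment. The treating investigator must notify the sponsor and "follow the pregnancy to term". As a separate instruction it adds: "The subject will continue to be followed as part of the mITT Population". The pregnancy is recorded as a protocol deviation, and "the subject will not be evaluated as part of the PP Population for timepoints after the pregnancy is confirmed".

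**Timing.** Protocol 12.7 requires a urine test at screening and before the initial and touch-up treatments. Protocol 4.3.4 places the optional touch-up 30 days after the initial injection, at the month 1 visit.

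**What follows a withdrawal.** Protocol 6.5 requires early-exit procedures, continued attempts to follow treatment-related adverse events that are ongoing, and a request for the subject's "permission to follow his/her status/ condition outside the study". Protocol 11.3 adds: "Any AE that is ongoing at the exit visit must be followed up as appropriate".

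**SAP.** It does not mention pregnancy. The primary analysis (SAP 5.1.3.1) uses the mITT population with no imputation.

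**The concern.** A site with a positive test at touch-up in a subject already injected can find support in the protocol for withdrawing her and for keeping her in the study. It cannot do both, and two sites could treat identical cases differently.

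The main stake is safety follow-up of a woman exposed to the device. New events are sought at study visits: "At each postscreening visit, the TI (or designee) will begin querying for AEs" (Protocol 11.1.1). If she is withdrawn at month 1, no scheduled visit remains at which a device event starting later would be asked about.

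A lesser stake is the month 6 score on the Allergan Chin Retrusion Scale (ACRS). For a treatment-group subject it would not be collected, and the primary analysis does not replace it.

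**Working it through.** **Step 1: which rule applies to whom (subject already injected unless stated).**

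| Situation | 6.6 applies? | 10.3 applies? | Conflict? |
|---|---|---|---|
| Positive test before any study treatment | Yes | No | No |
| Conceived before the initial injection, first positive at touch-up | Yes | No, since she did not become pregnant after treatment | No |
| Conceived after the initial injection, positive at touch-up | Yes | Yes | **Yes** |
| Conceived after treatment, found away from a treatment visit | No | Yes | No |
| Conceived after treatment, positive at the repeat visit | Yes | Yes | In wording, but little is lost |

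In the last row, month 12 procedures are complete before any repeat injection (Protocol 4.3.4). SAP 5.1.2.2 counts a treatment-group subject who completes month 12 without repeat treatment as a completer. The case with consequences is therefore the third row.

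**Step 2: scheduled follow-up lost if 6.6 is followed at touch-up.** Inputs are Protocol 4.2 (12 months after last treatment in the treatment group, 6 months for a control subject after optional treatment) and 4.3.4 (touch-up at month 1). She gets no touch-up, so her last treatment is the initial injection.

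- Treatment group: (12 − 1)/12 = 11/12 = 91.7%. The later visits named in readable text are month 3 (SAP 5.1.1.4), month 6 and month 12, so at least 3.
- Control subject after optional treatment: (6 − 1)/6 = 5/6 = 83.3%. No primary data are lost, because her control-period month 6 assessment is already done.

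These are shares of one affected subject's schedule, not of the trial's data.

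**Step 3: effect on the primary result.** Inputs are Protocol 8.5: 120 versus 40 subjects, 80% versus 40% responders, two-sided Fisher's exact test at 5%.

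The plan's own figure comes first. Exact enumeration gives power of 99.53%, which agrees with the stated figure of more than 99%.

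Planned responders are 0.80 × 120 = 96 and 0.40 × 40 = 16. The documents give no pregnancy rate, so 0 to 3 lost scores is an assumed range.

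| Scores lost | If all were responders | If all were non-responders |
|---|---|---|
| 0 | 96/120 = 80.0% | 96/120 = 80.0% |
| 1 | 95/119 = 79.8% | 96/119 = 80.7% |
| 3 | 93/117 = 79.5% | 96/117 = 82.1% |

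Fisher p against 16/40 is 5.5 × 10⁻⁶ with none lost, and 7.1 × 10⁻⁶ or 1.3 × 10⁻⁶ with three lost. Exact power with 117 treated subjects is 99.57%. The slight rise over 99.53% reflects the discreteness of the exact test.

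**Step 4: do the sensitivity analyses recover her score?** Not reliably.

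- SAP 5.1.1.4 applies both multiple imputation and last observation carried forward (LOCF) to subjects who have no postbaseline value.
- Its imputation model has a month 1 ACRS term, so a photo score at month 1 is expected. She may therefore have a postbaseline value from month 1 or early exit, and on the literal rule neither method would fill her month 6 score.
- Using the ITT population does not restore a missing score either. The responder method in SAP Table 5-2 counts only subjects with values at both baseline and the analysed visit.

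**The case against.** The strongest reply is that the two sections can be read together. On that reading 6.6 is the specific rule for pregnancies found at a treatment visit and 10.3 the general rule for the rest. The cross-reference in 6.6 suggests they were meant to work together: withdraw her, then follow the pregnancy. The mITT wording in 10.3 could be a mere classification, since one injection is enough for membership and withdrawal does not undo it.

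This is possible, but the text does not state it. 10.3 orders follow-up of the subject in addition to follow-up of the pregnancy. It also limits the per-protocol exclusion to timepoints after confirmation, which presupposes later study assessments. No readable sentence gives 6.6 precedence.

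Several other objections stand and limit the point:

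- The visit procedures between Protocol 6.1.2 and 6.3 and some exclusion criteria cannot be read in the public version. They may resolve the overlap.
- The case is narrow. It needs conception within about 30 days of the first injection, early enough to test positive, in a subject who presents for an optional touch-up.
- A withdrawn subject is not abandoned. Besides the provisions in 6.5, 10.3 and 11.3, Protocol 6.3 tells subjects to report unexpected symptoms.
- Whether a pregnant subject should keep attending is partly a policy choice for the sponsor.

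**Conclusion.** The conflict holds for one narrow case on the readable text: already injected, conceived after the initial injection, positive at touch-up. It is minor. Its cost is about 11 of 12 months of scheduled visits for an affected treatment-group subject (5 of 6 for a treated control), and possibly different handling at different sites. Confidence is medium, because unreadable visit text could settle the question.

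A reader might infer three stronger things that the documents do not support:

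- **That every positive test at touch-up triggers both rules.** A subject who conceived before her first injection falls under 6.6 only.
- **That withdrawal ends all safety tracking.** Ongoing events and the pregnancy are still followed. What is lost is scheduled detection of new events.
- **That the primary result is at risk.** With an assumed 0 to 3 scores lost, the planned responder rate stays between 79.5% and 82.1% and p stays below 0.00001.

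The opposite comfort, that multiple imputation and LOCF would cover her missing score, is not secure either, because of the condition attached to both. None of this changes the judgement that the effect on the primary result is negligible.

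**What to change.** Amend Protocol 6.6 to separate the two situations in one sentence: a subject who tests positive before any study treatment is not treated and is withdrawn, while a subject who has already been treated receives no further study treatment and stays in scheduled follow-up under 10.3. This keeps the protective purpose of 6.6. It also turns on whether she has been injected, which the site knows, and not on the date of conception.

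Limiting 10.3 to pregnancies found outside treatment visits would also remove the conflict, but the scheduled visits would still be lost.

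The cost is a one-sentence amendment with sponsor and IRB approval (Protocol 12.2), and continued visits that the subject may decline. This fix needs no SAP change: a month 6 score, once collected, already belongs in the mITT analysis.

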8.1 Analysis Populations

The following analysis populations will be used in the analyses for this study:

- intent-to-treat (ITT) population: all randomized subjects
- modified intent-to-treat (mITT) population: subjects who are randomized to study treatment (treatment group) and receive at least 1 study device treatment or are randomized to the control group
- per-protocol (PP) population: all mITT subjects who do not have any significant protocol deviations affecting the primary effectiveness endpoint
- safety population: all subjects randomized to treatment (treatment group) who receive at least 1 study device treatment and all subjects randomized to control group

Unless specified otherwise, all effectiveness analyses will be performed on the mITT population using the “as-randomized” assignment for each subject (ie, if a subject randomized to the control group is treated inadvertently at the start of the study, the assessments for that subject will nonetheless be included in the control group analysis). The ITT and PP populations as well as missing data imputation will be used to perform sensitivity

analyses for the primary effectiveness variable. Additionally, sensitivity analysis will be performed on mITT subjects with a baseline ACRS photo score of 2 or 3. All safety analyses will be conducted using the safety population.

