5.1.3.1 Primary Effectiveness Endpoint

The primary effectiveness endpoint will be met if the responder rate at month 6 for the treatment group is statistically greater than that for the control group at month 6 and the observed responder rate at month 6 for the treatment group is greater than 50%. A responder is a subject who shows clinically significant improvement, i.e., ≥ 1 -point decrease, on the ACRS from baseline based on EI assessment of 2D renderings of the chin profile.

The primary effectiveness analysis is summarized in Table 5-15.

Table 5-15 Primary Effectiveness Analyses

Endpoint	Description	Timing	Methodology
Primary: Responder analysis based on photo ACRS	
• Superiority of the treatment group over no-treatment control group• Responder rate of treatment group is greater than 50%	Month 6	Responder

The primary effectiveness analysis will be performed on the mITT population without any missing data imputation. Sensitivity analysis will be performed using ITT and PP populations as well as using missing data handling conventions as described in Section 5.1.1.1.4. Additionally, sensitivity analysis will be performed on mITT subjects with a baseline ACRS photo score of 2 or 3.

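### Subjects withdrawn under Protocol 6.6 before the month 6 window will generally drop out of the responder rate, and no planned analysis says how they count

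*Protocol*

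**What the plan says.** Protocol 6.6, after dealing with pregnancy, lists three procedure events that end study participation: "In addition, a subject must be withdrawn from the study if he or she" undergoes a facelift or facial reconstructive surgery, "receives any dermal filler or fat injection to the chin area", or "receives treatment with hyaluronidase in the chin area". Protocol 4.4.3 separately says of reversing misplaced or excess filler that "administration of hyaluronidase for this use should not be performed during this study". Protocol 4.4.2 nevertheless accepts that a prohibited treatment may be given when the subject's safety calls for it.

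For a subject who leaves, Protocol 6.5 adds: "The month 12/early exit procedures are to be performed at the final study visit". SAP 6.2 assigns every dated visit, scheduled or not, to an analysis window.

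On the analysis side, SAP 5.1.3.1 states: "The primary effectiveness analysis will be performed on the mITT population without any missing data imputation". The responder method in SAP Table 5-2 limits the count to subjects with non-missing values at both baseline and the visit analysed. SAP Table 5-3 offers multiple imputation and LOCF as sensitivity analyses only, and words both for subjects who have no post-baseline value at all.

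Protocol 8.1 (repeated in SAP 5.1.1.1) says of a control injected by mistake at the start of the study that "the assessments for that subject will nonetheless be included in the control group analysis".

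**The concern.** A subject whose gel is dissolved before month 6 no longer has the treatment effect that the endpoint measures. If that subject exits without a month 6 score, the primary analysis drops the subject from both numerator and denominator. Nothing visible in either document says whether the subject is a non-responder, is missing, or is handled in some other way. The loss may then depend on the outcome. For hyaluronidase it also depends on arm, because during the control period essentially only treated subjects have gel to dissolve. The quantity affected is the treatment-arm responder rate, which is both compared with control and held against the 50% floor.

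The wording also raises a smaller question. Protocol 9.1.1 describes the study device itself as a dermal filler. Read literally, the filler trigger in 6.6 would withdraw the very control whose assessments 8.1 says are kept.

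**Working it through.** **Reproducing the plan's figure.** Inputs from Protocol 8.5 and SAP 5.2: 120 treated and 40 control subjects evaluable, responder rates 80% and 40%, two-sided Fisher's exact test at 5%. Summing over both binomial distributions gives power of 99.5%, and the same to that precision when the 50% floor is added. The plan's figure of more than 99% is confirmed.

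**Do the sensitivity analyses recover these subjects?**
- The ITT and PP sets change who is eligible but do not supply a missing score.
- Read literally, multiple imputation and LOCF exclude anyone with a month 1 or month 3 score, although the imputation model uses those two scores as predictors.
- Read more generously, LOCF would carry forward, and the imputation would condition on, month 1 or 3 scores that may predate the event. A subject whose gel was dissolved at month 4 could then be scored a responder.

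**Size.** Let *f* be the share of the treatment arm that has such an event, leaves without a score and is regarded as non-responding. Then

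rate with them counted = observed rate × (1 − *f*).

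The documents do not give *f*. The range below is an assumption, from 0 up to the whole planned 15% dropout: 120/0.85 ≈ 141, so 21 subjects. Observed responders are 96/120, and control is 16/40.

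| Withdrawn, counted as non-responders | Treatment rate | Fisher p vs 16/40 |
|---|---|---|
| 0 | 96/120 = 80.0% | 0.000005 |
| 2 | 96/122 = 78.7% | 0.00001 |
| 4 | 96/124 = 77.4% | 0.00002 |
| 10 | 96/130 = 73.8% | 0.0002 |
| 21 | 96/141 = 68.1% | 0.0017 |

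In the last row, if the 7 missing controls (40/0.85 ≈ 47) were also all responders, the comparison is 96/141 against 23/47 (48.9%), p = 0.023. To fall from 80% to the 50% floor needs *f* = 1 − 0.50/0.80 = 37.5%.

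**Near a boundary.** A few subjects can matter only if the result is already marginal.
- At the planning control rate of 16/40, the smallest significant treatment count is 71/120 (59.2%, p = 0.044). Four added non-responders give 71/124 (57.3%, p = 0.069).
- The floor decides only if control responds less than planned. With an assumed 12/40 (30%), 61/120 (50.8%, p = 0.028) passes, while 61/124 (49.2%, p = 0.044) fails the floor.
- At 16/40, 61/120 gives p = 0.27, so superiority has already failed and the floor is irrelevant.

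**The case against.** **The score need not be missing.** A reader might infer that every withdrawn subject lacks a month 6 score. The documents do not support that. An exit visit inside the month 6 window could supply one, and an event after month 6 cannot affect the endpoint. The content of the exit visit and the window limits are not visible. This stands, and it is why the point is limited to subjects who leave before the window.

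**The event should be rare.** Protocol 4.4.3 says reversal with hyaluronidase should not be performed, so the clearest case is a departure from protocol. This also stands. Yet 6.6 lists the event, so the plan foresees it and should say how it counts.

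**These are not all failures, and not all favour the device.** A reader might infer that 6.6 simply removes treatment failures. The documents define no such status. Dissolving excess gel is not the same as too little projection, added filler could improve the score, and filler, fat or a facelift can occur in untreated controls. If those controls would have counted as non-responders, dropping them raises the control rate and works against the device. Only hyaluronidase has a clear direction, and only if non-response is the chosen reading.

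**Conflict with the as-randomized rule.** A reader might see a general contradiction. The rule fixes the arm in which a subject is counted; it does not require follow-up after withdrawal. The clash is confined to the inadvertently injected control. Taken fully literally, the filler trigger would withdraw every treated subject, so non-study filler is probably meant, but the text does not say so.

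**Safety follow-up.** A reader might infer that these subjects are lost for safety. Protocol 6.5 covers follow-up "If an AE is ongoing at the time of withdrawal and is related to the study treatment", section 11 covers ongoing treatment-related serious events, 11.3 any event ongoing at exit, and 11.4 all subjects with a serious event. Only events that begin after exit appear uncovered, and the point does not rest on that.

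**Conclusion.** The concern holds as a gap in the analysis rules. The plan foresees an event that can remove subjects from the primary endpoint for reasons tied to the outcome, does not say how they count, and offers sensitivity analyses that do not clearly reach them or may use scores from before the event.

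The likely size is small: about 0.8 percentage point for each 1% of the treatment arm affected, at an 80% observed rate. At the planning rates neither success criterion changes, even if the whole planned treatment-arm dropout were of this kind. It could matter only for a marginal result. These figures assume that such subjects exit without a score in the month 6 window and are regarded as non-responders; their number is unknown.

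**What to change.** 1. In SAP 5.1.3.1, add a named sensitivity analysis of the primary endpoint in which treatment-arm subjects with a 6.6 procedure event before month 6 count as non-responders. Run it with controls under the same rule and, alternatively, with controls at their observed month 6 score where there is one.
2. In SAP Table 5-3, change the scope of multiple imputation and LOCF from subjects without any post-baseline value to subjects without a month 6 value. State that pre-event scores are not used for subjects with a 6.6 procedure event.
3. Reconcile Protocol 6.6 with 8.1 by stating whether the filler trigger includes study device given inadvertently to a control.

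The cost is SAP wording, one short clarification in the protocol and a little more analysis. The treatment responder rate in the added analysis may be slightly lower. No change to any withdrawal, treatment or stopping rule is proposed.
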